Parents will be screened to be sure they qualify to participate in the study (See attached Screening Form). Parent(s) will read, have the opportunity to ask questions about, and sign the informed consent form and the HIPPA Authorization Form. Each parent who agrees to participate will complete a Participant Information Form with information about their own height, weight, age, race/ethnicity, primary language, and family history. They will also provide the phone number to their mobile device on the data collection sheet, their child's date of birth, and indicate if they will be answering the surveys since only one parent will be permitted to answer the surveys. To participate, at least one parent must agree to answer the surveys. Then, the participants will be randomized to one of the following groups: feeding text messaging or usual care with safety text messaging. A computer-generated blocked randomization schedule with balanced distribution with regards to sex will be used to place

infants into groups. This stratified allocation will be concealed in opaque, sequentially-numbered sealed envelopes, and opened by study staff. While parents recruited may vary in weight status, income, and race/ethnicity, in a pediatric primary care setting randomizing participants into groups based on these multiple criteria, which are not gathered on parents of patients would be burdensome for clinic staff. Thus, parent participants will be randomized into each study group (usual care or text-messaging) based only on sex of the infant.

After research staff know the group assignment, they will enroll parents into the study using the child’s date of birth and the parents’ mobile phone numbers. See the figure below for the sequence of enrollment events.

[figure not shown]

Figure 1: Flow and Sequence of Enrollment Events

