Parents will have the opportunity to opt out of the messages by replying “STOP” at any time. Opting out will be viewed as non-participation. Short (less than 160 character) text messages will be provided at scheduled intervals. Parents who indicate their infant will be breastfeeding will receive messages aimed at supporting breastfeeding. Parents who indicate their infant is receiving formula will receive messages aimed at supporting appropriate formula feeding. When babies/parents are ready to start solids, the parents will text “solids” to 41411 to begin receiving messages pertaining to feeding their baby solids. Messages will offer motivational, gain- or loss- framed, feeding-related messages, which will not convey information regarding past, present or future medical conditions or care. Some messages will contain links to a parent landing page (Web page), where parents may read content with more information on feeding advice. The landing pages will also contain links to appropriate external web pages with additional information or videos related to feeding and infant nutrition care. The text messages will be delivered using a service called Healthy-Txt, which is in use in other pediatric primary care settings (such as UCLA) to provide appointment reminders and other messaging.⁵⁶ TWU nutrition and health studies professors, UNT-HSC pediatricians, nutrition graduate students, and a TWU communications professor specializing in feeding assisted with development of the text-messaging content and Web landing page materials. Participants will not be able to respond to texts. Participants will receive a text with the first text in each group to “Remember to call 911 in a medical emergency”.

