Texas Woman’s University’s IRB will rely on the North Texas Regional IRB and will sign an Institutional Authorization Agreement upon approval of the study by the North Texas Regional IRB . ([name], IRB Coordinator, [contact]; [contact])

5) *Laboratory methods and facilities* - N/A

6) *Estimated Period of Time to Complete the Study* –

Task	Year 1 (September 30, 2018-August 31, 2019) Quarters (3-months)				Year 2 September 30, 2019- February 28, 2020 Quarters (3-months)	
	9/30-11/30	12/1-2/28	3/1-5/31	6/1-8/31	9/1-11/30	12/1-2/28
Participant Recruitment	X					
Data Collection	X	X	X	X	X	
Data Analysis		X	X	X	X	
Manuscript Preparation						X

F. Human Subjects - Describe the characteristics of the research population:

1) *Sample Size*: 30-40 parent/infant dyads. Both parents may participate and receive separate text messages, but one compensation item will be provided per family.

2) Describe both *Inclusion / Exclusion Criteria*.

Inclusion criteria will be:

- Parents with age 18 and older. We don’t include parents younger than 18 because it is suspected that their concerns regarding feeding and sources of feeding advice may be different compared to adult parents.
- Healthy and term infants (born at 37 weeks or later) establishing care with the healthcare provider between 3-30 days of life and their infants (Parent/infant dyads).

- Parents must be able to speak and read English well. All researchers speak only English, thus we would like to pilot this in an English-speaking population first to make sure the messages are well crafted.
- Parents must have a mobile phone that can receive text messages and access the Internet.

Exclusion criteria will include:

- Infants with congenital anomalies, genetic disorders, or who develop failure-to-thrive during the intervention

3) Describe intended *gender, age range, intended racial and ethnic distribution*.

Both fathers and mothers are sought for participation. However, only one parent may fill out the questionnaires and will receive incentives for their participation. Participants must be adult parents of infants, but there is no upper age limit for participation. Because of the make-up of the clinic population, it is thought that about half of participants will be Hispanic to reflect the clinic population.

4) Identify the *source(s) from which you will obtain your study population*. All participants will be parents of infants and their infants attending the UNT-HSC Pediatric Clinic.

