There is an informational risk associated with participation due to possible breach of confidentiality or loss of privacy. To prevent loss of confidentiality each participant completing the survey through PsychData will receive a unique respondent ID number. Data on demographics, language spoken, and other personal information on the participants will be collected, stored, and accessed separately and then linked using secure methods. The information on the infant's age, weight, and height gathered from the electronic medical record (EMR) will be stored in a spreadsheet together with the randomly assigned participant ID number. No identifying information will be stored together with the MRN on the master list. The master list will be stored on a secure drive in the UNTHSC department of pediatrics. Only the PI and the research coordinator assigned to the project will have access to the master list. The de-identified spreadsheet with the infant age, height, and weight data will be shared with the TWU collaborators and research staff for analysis. Information from the 24-hour recall will be recorded on a data collection form with only the randomly assigned participant ID number and when analyzed will be stored in a

spreadsheet with only the randomly assigned participant ID number. Data being analyzed by the researchers at UNTHSC or TWU will be a de-identified set of data.

There is also an emotional risk associated with survey completion if evaluating text messages provokes an unwanted, emotional response. At the beginning of the survey, participants will be notified that they may exit the survey at any time without penalty. On the last page of the survey, participants will be advised to contact the co-investigator if they have problems, and they will also be given a link to click which will include resources if they need assistance with an emotional response.

There is a risk of loss of time. Reading text messages is voluntary, even for parents who have agreed to participate. Time spent in this activity is up to the discretion of the participants and will likely be useful to those parents who decide to spend time in this way. Time spent completing surveys will be kept as minimal as possible to achieve the stated research goals. Parents will be able to complete them using their mobile devices during their child's healthcare visit or afterwards if needed at their convenience. Participants will be compensated for their time and effort.

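### Support for the named emotional risk is placed on the last survey page, so a parent who uses the offered early exit because of distress does not reach it through the survey

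*Protocol*

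**What the plan says.** Section G (Risk/Benefit Assessment), item 4, names the risk: "There is also an emotional risk associated with survey completion if evaluating text messages provokes an unwanted, emotional response". Two measures follow. The first comes at the start: "At the beginning of the survey, participants will be notified that they may exit the survey at any time without penalty". The second comes at the end: "On the last page of the survey, participants will be advised to contact the co-investigator if they have problems". The same sentence adds that "they will also be given a link to click which will include resources if they need assistance with an emotional response".

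Three other parts of the protocol bear on this:

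- Section E.1 describes the surveys as feeding questions adapted from a national dietary questionnaire, with added items on responsive feeding. They are given at four time points. Section E.2 says that a research statement comes before each survey, but its wording is not shown.
- Section E.1 says of the texts with feeding advice: "Messages will offer motivational, gain- or loss- framed, feeding-related messages".
- Section F.1 says "Both parents may participate and receive separate text messages", while section E.1 says "only one parent will be permitted to answer the surveys".

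**The concern.** The two measures work against each other for the parent they are meant to protect. Leaving early is the natural response to an upsetting question, and the protocol rightly permits it. But leaving early also means never reaching the page with the contact and the link. As written, the support is sure to reach parents who finish the survey and may miss those who stop because of it.

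A second, smaller problem is that the risk is described through an activity that the trial surveys, as set out in section E.1, do not contain. If the risk statement does not match what parents are asked to do, it is hard to judge whether the safeguard sits in the right place.

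What is at stake is modest participant protection. No estimate, test or endpoint depends on it.

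**Working it through.** No arithmetic applies. The protocol gives no rate of distress or of leaving a survey midway. The check is a reading of the relevant sections side by side.

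1. **Order of events in one survey (sections E.2 and G.4).** The research statement comes first. The exit notice comes at the beginning, then the questions, and the contact advice and link come on the last page. A parent who completes the survey sees everything. A parent who leaves at any question before the last page sees the exit notice but not the contact advice or the link. This follows from the stated placement alone.

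2. **Other contact points in the visible text.** Section E.1 includes a text about calling the emergency number in a medical emergency, and says that participants cannot respond to texts apart from opting out or sending set keywords. The reminder for unfinished surveys, also in E.1, gives a contact and invites a reply, but for switching message groups. Section E.4 allows the survey to be completed before, during or after the visit, or from a texted link, so staff need not be at hand. None of these is offered as help with an emotional response.

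3. **What cannot be seen.** The consent form is a separate document, some text was removed before review, and the wording of the research statement is not given. Any of these may hold a contact or resources. The finding is therefore limited to where section G.4 itself puts the support.

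4. **Wording of the risk.** Section G.4 ties the risk to evaluating text messages. Section E.1 describes surveys on feeding practices and responsive feeding, with no rating of messages. A survey about messages does appear in section C, as preliminary work. The sentence may have been carried over from there, but that is an inference.

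5. **Who is exposed.** The named risk arises from completing a survey. The one parent per family who answers the surveys is exposed to it, up to four times. A second parent who receives only texts is not exposed to the risk as the protocol defines it.

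**The case against.** The strongest reply is that this is a minimal-risk study with feeding questionnaires, and that free exit without penalty is itself a safeguard. Reading the texts is voluntary, parents can stop them, and families meet staff at visits and speak to them in the recall calls. The consent form or the research statement may already give a contact. Most of this stands. It makes the point minor and rules out saying that support is absent. It does not remove the mismatch in section G.4, which names the mitigation for this risk and places it where an early leaver will not see it.

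A reader might infer three stronger points that the documents do not support:

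- **Second parents are left without support for this risk.** They receive texts and answer no survey, so they never see the last page. But the named risk is tied to survey completion, so they are not exposed to it. The same holds for a parent who skips a survey. Distress from the texts is a different risk, which the visible text does not name.
- **The risk is wholly unmitigated.** That cannot be shown while the consent form and the research statement are unseen.
- **The gap can be sized from the 30% dropout allowance or from the number of texts.** The dropout figure in section E.2 inflates the sample size and is not a rate of leaving a survey midway. The number of texts does not measure a risk that arises from surveys.

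**Conclusion.** The point holds in a narrow form. In the protocol text shown, the contact advice and the resources link for the survey-related emotional risk are on the last page, and a parent who exits early because of distress does not reach them through the survey. The risk sentence also does not match the surveys described in section E.1.

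Severity is minor. The size cannot be estimated from the documents. It depends on how often distress leads to early exit, which is not given and may be rare. The conclusion assumes that the survey is built as section G.4 describes, with the contact and link not also shown before the questions or on exit. If the research statement or an exit screen already carries them, the placement problem is solved, and only the wording and a short cross-reference in section G.4 remain to be corrected.

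**What to change.** - Show the co-investigator contact and the resources link in the research statement that already precedes each survey, and again on exit, while keeping them on the last page. State this in section G.4.
- Reword the risk sentence so that it refers to the feeding questions parents actually answer.
- Decide whether the risk should also cover the text messages. If so, put the same link in the initial text or on the landing page, so that parents who answer no survey can see it. The initial text is the surer route: both groups receive it, whereas section E.1 describes the landing pages as carrying feeding advice. A short link would respect the stated limit of under 160 characters.

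The cost is a slightly longer opening page, small edits to the survey template and possibly one text, and a minor IRB amendment. No visits, staff time or data collection are added. The same wording in both groups leaves the comparison unaffected.
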